9.2 Halting Rules

If any participant experiences a study drug-related SAE in the 24 hours following methadone administration, then study dosing administration will be stopped. The DSMB will be notified and will conduct a review, study activities will be allowed to proceed on previously enrolled and new participants.

If 3 or more of participants enrolled to date experience a severe (Grade 3 or higher) reaction related to the study drug, then the study will be halted for DSMB.

Refer to Section **5.3** for requirements of participant safety follow-up following cessation of study product/intervention.

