8.2 Guidelines for Assessing Association of an Adverse Event

A **serious adverse event (SAE)** or **serious suspected adverse reaction** or **serious adverse reactions** determined by the investigator or the sponsor is an AE or SAR that results in any of the following outcomes:

- Death
- Life-threatening AE (“life-threatening” means that the study participant was, in the opinion of the investigator or sponsor, at immediate risk of death from the reaction as it occurred and required immediate intervention)
- Persistent or significant incapacity or substantial disruption of the ability to conduct normal life functions
- Inpatient hospitalization or prolongation of existing hospitalization
- Congenital abnormality or birth defect
- Important medical event that may not result in one of the above outcomes, but may jeopardize the health of the study participant or require medical or surgical intervention to prevent one of the outcomes listed in the above definition of serious event.

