8.6 Safety Event Follow-up and Sponsor Reporting

Adverse Events, SAEs, and SESIs **directly related** to study intervention/procedures will be followed until resolution, even if this period extends beyond the study-reporting period.

Resolution of an AE is defined as the return to pretreatment status or stabilization of the condition with the expectation that resolution will remain chronic. If the event resolves during the study or follow-up period, a resolution date should be documented in the data system.

Adverse Events **directly related** to study intervention/procedures and SESIs (without a causal relationship to study intervention, that are not defined as an SAE) will be reported in the data system within 7 days of identification/site awareness.

Adverse Events considered related to study intervention/procedures and all SAEs/SESIs ongoing at the time of the last dose of study intervention will be followed for as long as necessary to adequately evaluate the participant's safety or until the event stabilizes. If the event resolves during the study or follow-up period, a resolution date should be documented in the data system.

Serious Adverse Events, SUSARs, and SESIs that are associated with any of the criteria that define the event as an SAE will be reported in the data system within 24 hours of identification/site awareness. Upon entry in the Electronic Data Capture (EDC) system, these events will generate an automatic email notification to the MM and the sponsor. The investigator/delegate (defined as a clinician licensed to make a diagnosis) must document his or her assessment of intensity, causality, and association in the participant records in a timely manner and submit safety reports as required by his or her IRB.

The MM will review all safety events at the time they are reported. Any event that requires expedited reporting based on federal regulations (21 CFR 312.32) will be forwarded to the IND sponsor. The IND sponsor or its representative will submit expedited safety reports (e.g., IND safety reports) to the regulatory agencies, as necessary.

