8.9 Data and Safety Oversight (Medical Monitor/Data Safety Monitoring Board)

The study will be monitored by the BPCA Data Safety Monitoring Board (DSMB). The NIH charters the DSMB to support all research activities conducted under the BPCA PTN.

In addition, the study has designated a qualified and experienced physician not otherwise associated with this protocol to serve as the Medical Monitor (MM) and review all safety events at the time they are reported and/or updated. The MM may request additional information regarding a site reported SAE; the Study PI is expected to provide requested information or materials to the MM in an expeditious manner to support the writing/submission of study safety reports. The MM will be available to study sites as needed. The study IND sponsor will also review all SAEs to determine regulatory reporting and will be available to sites as needed.

If safety concerns are identified, the MM may request a meeting of the DSMB to review safety data. The MM will also provide an initial report to the PTN PI/IND sponsor and an unbiased written report to the DSMB of the event per the DSMB charter/safety monitoring plan. At a minimum, the MM will comment on the outcomes of the safety event and the relationship of the safety event to the study product/intervention. The MM will also indicate whether they concur with the details of the report provided by the study site investigator. If no safety events prompt review at an earlier time point, the DSMB will review safety events per the DSMB charter.

The DSMB will convene and make recommendations on termination of the study based on review of safety reports and halting rules. The safety data will be compiled by the TDS. Based on the recommendations of the DSMB, PTN, and NIH/NICHD, the IND sponsor will decide to terminate or continue the study.

Ad Hoc Meetings of the DSMB: The DSMB may convene an ad hoc meeting to discuss any issue of data and safety raised by the site investigator, MM, the IND sponsor, NICHD, or a member of the DSMB. At the discretion of the investigators, the IND sponsor, NICHD, and DSMB members, a non-serious safety event that is associated with the product or procedures may be considered as a trigger for an ad hoc DSMB meeting to assess the safety of the product/intervention, without resulting in halting the enrollment of the trial.

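### Severe drug-related reactions count toward halting rule 2 even when non-serious, but section 8.6 lets them reach the medical monitor up to 6 days later than serious events

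*Combined protocol and SAP*

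**What the plan says.** Section 9.2 of the protocol has two halting rules.

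- **Rule 1** depends on seriousness: "If any participant experiences a study drug-related SAE in the 24 hours following methadone administration, then study dosing administration will be stopped". Its next sentence provides for DSMB review and then says that study activity may go on, both for people already enrolled and for new ones. It does not say whether that waits for the review.
- **Rule 2** depends on severity and relatedness: "If 3 or more of participants enrolled to date experience a severe (Grade 3 or higher) reaction related to the study drug". The study is then halted for the DSMB. Seriousness is not a condition.

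Section 8.6 sets two reporting limits. Adverse events directly related to the intervention or procedures "will be reported in the data system within 7 days of identification/site awareness". SAEs, SUSARs and safety events of special interest that meet an SAE criterion must be entered within 24 hours, and "these events will generate an automatic email notification to the MM and the sponsor". The email is tied to that second group only.

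Under section 8.9 the MM, a physician independent of the protocol, is to "review all safety events at the time they are reported and/or updated". For the sponsor, 8.9 states: "The study IND sponsor will also review all SAEs to determine regulatory reporting". If safety concerns are identified, the MM also sends the sponsor an initial report, with no time limit. The sponsor is among those at whose discretion "a non-serious safety event that is associated with the product or procedures may be considered as a trigger for an ad hoc DSMB meeting".

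Section 8.2 defines an SAE as one "determined by the investigator or the sponsor is an AE or SAR that results in any of the following outcomes", so the sponsor as well as the investigator can call an event serious.

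**The concern.** Severity (8.3) and seriousness (8.2) are separate scales, so a reaction can be severe, drug-related and non-serious. The protocol treats such a reaction as important enough to count toward a halt, yet reports it on the same slow path as a trivial related event.

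The two scales meet at a point of judgement. In 8.3 an event is severe if it needs significant intervention. One SAE criterion in 8.2 is that intervention was needed to prevent a serious outcome. Where a site grades an event severe but not serious, a second opinion from outside the site has most value, and that opinion has no short clock. At stake is prompt outside review of the first and second such reactions, in healthy volunteers who expect no benefit (2.3). That review includes whether an event should be classed as serious and so come under rule 1.

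**Working it through.** The plan gives no figure of its own for this lag, so there is none to reproduce. The inputs are the two limits in 8.6, the 24-hour window and the count of three in 9.2, and the inpatient stay of about 30 hours in 6.3.

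**Step 1. Which path applies.**

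| Reaction (drug-related, severe) | Counts for rule 2 | Entry limit (8.6) | Automatic email to MM and sponsor (8.6) | Sponsor review stated (8.9) |
|---|---|---|---|---|
| Serious | Yes | 24 h | Yes | Yes |
| Not serious | Yes | 7 days | No | No |

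Section 8.3 names three intensity levels without numbers. I take its severe level and the grade in rule 2 to mean the same thing.

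**Step 2. Maximum extra lag to MM review.** MM review follows entry, and both limits run from site awareness.

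- Non-serious: 7 × 24 = 168 h
- Serious: 24 h
- Difference: 168 − 24 = 144 h; 144 / 24 = 6 days

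**Step 3. Position relative to the dose.** Take a reaction in rule 1's window, 0 to 24 h after dosing, and assume the site notices it at onset because the participant is an inpatient.

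- Present deadline: 0 + 168 = 168 h to 24 + 168 = 192 h after that dose (7 to 8 days)
- On the 24-hour path: 0 + 24 = 24 h to 24 + 24 = 48 h after that dose
- Difference: 144 h at both ends

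**Step 4. The sponsor.** No clock is stated for a non-serious event, so no delay can be calculated. The MM's initial report comes after MM review, so it cannot shorten the lag in step 2.

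**Step 5. Effect on the halting rules.** Rule 2 needs three participants, so 3 − 1 = 2 reactions can occur before it acts. The rule does not depend on data entry. The site sees every event, and the rule binds it at the third. The lag therefore adds 0 days to a rule 2 halt.

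**Step 6. Participants dosed meanwhile.** The documents give no dosing pace. At assumed paces of 1, 2 or 4 participants a week, weekly pace × 6/7 gives 0.86, 1.71 or 3.43 dosed in 6 days. These show scale only. They do not count participants exposed because of the lag, since nothing shows that earlier review would have stopped dosing.

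**The case against.** The strongest reply is that nothing in the halting scheme fails. There is one site, it knows its own count, and 16.2 has the Study PI or designee review adverse event assessments. Seven days is a ceiling on data entry. It does not stop the site from calling the MM, who is available to sites under 8.9, and the site investigator can raise any issue for an ad hoc DSMB meeting. Section 8.6.1 requires MM notice when an adverse event leads to withdrawal. The DSMB charter and safety monitoring plan are not supplied and may set a faster route. All of this stands, and it makes the point minor. It does not remove it: the calls and meetings are discretionary, and the withdrawal notice has no deadline and covers only withdrawals.

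Four stronger readings are tempting, and the documents do not support them.

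- **That dosing could run past the third reaction because entry is slow.** Rule 2 acts on reactions experienced, not on reactions entered.
- **That the sponsor is cut off.** The MM's initial report in 8.9 is a stated route, though conditional and untimed.
- **That an upgrade to serious would cleanly turn a three-event stop into a one-event stop.** Rule 1's second sentence leaves unclear how far dosing stops.
- **That respiratory depression reversed with naloxone could wait a week.** Section 2.4 lists it as a potentially life-threatening hazard, and needing intervention to prevent a serious outcome is an SAE criterion in 8.2. It would probably already be on the 24-hour path.

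**Conclusion.** The mismatch is real and small. For a severe, related, non-serious reaction, the latest permitted MM review is 144 hours (6 days) later than on the path the protocol already has for serious events, and the sponsor has no automatic alert. What is lost is timely outside review of up to two reactions before rule 2 acts. No rule 2 halt is delayed.

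The size rests on three assumptions: that the site uses the full time allowed, that the MM hears by no other route first, and that no unsupplied document sets a shorter limit. The 7-to-8-day figure after dosing also assumes awareness at onset. The number of such reactions cannot be estimated from the documents, and many severe reactions will be SAEs in any case. I would list this as a cheap improvement, not as a flaw in the halting rules.

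**What to change.** In 8.6, extend the list of events entered within 24 hours of awareness, with automatic email to the MM and sponsor, by adding: 'and any severe adverse event considered related to study drug, whether or not serious'. Leave the thresholds in 9.2 unchanged.

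The maximum time from site awareness to MM visibility then falls from 168 h to 24 h for these events, and the sponsor gets the same email as for an SAE. The cost is one phrase, one notification setting in the data capture system and quicker entry of a few events. It adds no hold before dosing. The alert would still depend on the site's own grading, so an event graded moderate or unrelated would not be caught.

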10 CLINICAL MONITORING

Clinical site monitoring is conducted to ensure that the rights and well-being of study participants are protected, that the reported study data are attributable, legible, contemporaneous, original, accurate, and complete, and that the conduct of the study is in compliance with the currently approved protocol/amendment(s), with ICH GCP [E6(R2)], and with applicable regulatory requirement(s) including 21 CFR 312 Subpart D Responsibilities of Sponsors and Investigators.

The Study PI, or as detailed in the Transfer of Regulatory Obligations, or his/her designee will conduct site-monitoring visits. Site visits will be made at standard intervals as defined by the clinical site monitoring plan and may be made more frequently as directed by the PTN Monitoring Team, IND sponsor and/or NICHD. Monitoring visits will include, but are not limited to, review of regulatory files, accountability records, data collection forms, informed consent forms, medical and laboratory reports, and protocol compliance. Study monitors will meet with investigators to discuss any problems and actions to be taken and document visit findings and discussions.

The study-specific clinical site monitoring plan will supplement the BPCA project-wide clinical monitoring plan based on protocol risk assessments.

11 STATISTICAL CONSIDERATIONS

Pharmacokinetics (PK), Pharmacodynamics (PD), and safety analyses will be conducted. Participant demographics will be summarized. In addition, the number of participants enrolled, completed, discontinued early from study, and the reasons for discontinuation will also be summarized.

Descriptive statistics, such as the number of observations, mean, median, 95% confidence interval, standard deviation, standard error, minimum, and maximum, will be considered for continuous variables (such as age, weight, etc.). Other descriptive statistics, such as counts, proportions, and/or percentages, will be presented to summarize discrete variables (such as sex, race, etc.).

11.1 Study Endpoints

11.1.1 Primary Endpoints

The list of primary endpoints includes the following:

- Clearance (CL)
- Volume of distribution (Vz)
- Half-life ($t_{1/2}$)
- Area under the curve (AUC)
- Maximum concentration (C_{max})
- Time to maximum concentration (T_{max})
- Minimum concentration (C_{min})
- Elimination rate constant (k_e)

11.1.2 Secondary Endpoints

The list of secondary endpoints includes the following:

- Change in pupillometry
- Observed sedation
- Thermal pain tolerance thresholds
- VAS from pre-dose to post-dose
- Proportion of participants reporting AE, SAE, SUSAR from baseline to the end of safety follow-up
- QTc from baseline to the end of safety follow-up

11.1.3 Exploratory Endpoints

The list of exploratory endpoints includes the correlation of plasma concentrations to VAS score at each post-dose VAS time point. Plasma concentrations are listed in the primary endpoints. Post-dose VAS time points are displayed in [Table 5](#).

11.2 Analysis Population

PK population: All enrolled participants who receive a dose of IV methadone and have at least one evaluable PK sample will be eligible for the PK analysis population.

Safety population: All participants enrolled who received a dose of IV methadone will be included in the safety analysis.

Efficacy (PK/PD) population: All participants enrolled who received at least one dose of IV methadone and provided at least one PK sample and a corresponding efficacy assessment will be included in the efficacy analysis.

11.3 Analysis Plan

Noncompartmental analysis will be conducted to determine methadone PK. Compartmental modeling may be explored. Additional details are in the statistical analysis plan.

Descriptive statistics, such as number of observations, mean, median, standard deviation, standard error, minimum, and maximum, will be presented for continuous variables (such as age, weight, etc.). Other descriptive statistics, such as counts, proportions, and/or percentages, will be presented to summarize discrete variables (such as race, sex, etc.). All descriptive analyses will be presented overall. A 95% confidence level will be used for confidence intervals. A detailed description of statistical methods and secondary analyses will be prepared and presented in the statistical analysis plan prior to data lock for final analyses.

11.3.1 Primary Analysis

The dosing, sampling, and demographic information recorded on the eCRFs will be merged with bioanalytical information to create a PK dataset for methadone. A noncompartmental PK analysis will be performed in Phoenix WinNonlin (version 6.3 or later) using concentration–time data of methadone in plasma. The PK parameters for methadone will be summarized using descriptive statistics, including arithmetic mean, standard deviation, minimum, median, maximum, and geometric mean.

Following the study dose on Day 0, peak drug concentration (C_{\max}), time at peak concentration (T_{\max}), and area under the concentration versus time curve (AUC) will be calculated using the observed data for methadone as appropriate and, if possible, depending on actual samples collected. AUC will be calculated using the linear trapezoidal method. At least 3 time points after the last dose with measurable plasma concentrations will be required for the calculation of AUC_{0-24} .

In addition, the following additional PK parameters will be estimated as appropriate and, if possible, depending on actual samples collected: apparent terminal elimination rate constant (k_e), terminal-phase disposition half-life ($t_{1/2}$), total clearance (CL), and volume of distribution during terminal phase (V_z). k_e will be determined as the slope of a log-linear least squares of at least 3 concentration–time points after the last dose judged, by visual inspection, to be in the apparent terminal elimination phase. Half-life will be calculated as $t_{1/2} = \ln 2/k_e$.

Nominal sampling time will be used in PK calculations, unless actual times are needed. If samples are below the quantification limit and occur prior to the time at C_{\max} , a value of zero will be assigned; for samples occurring after C_{\max} , half the quantification limit will be assigned for a single below-quantifiable-limit sample, or zero for all values in consecutive samples that are below quantifiable limit.

Compartmental methods will also be explored. Please see the PK analysis plan (PKAP) for additional details.

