Russell et al. 2013 ²³	75 Adult women - 25 methadone - 50 control	fentanyl, morphine, fentanyl and morphine	Caesarean delivery	The methadone group had lower pain scores and decreased opioid requirements immediately postoperatively, as well as decreased opioid use over 48 hours.
Gottschalk et al. 2011 ²⁴	30 Adults (18 – 75) - 13 methadone	Sufentanil	Spinal fusion	The methadone group had decreased pain scores at 48 hours

	- 16 sufentanil			and decreased opioid usage at 48 hours compared to the sufentanil group .
--	-----------------	--	--	---

Methadone was, however, developed and approved long before the regulatory requirements for pharmacokinetic (PK) and pharmacodynamic (PD) characterizations and numerous *in vitro* and *in vivo* preclinical and clinical studies, which are required today for drug approvals. While some investigations in the past few years have discovered missing information regarding methadone biotransformation, drug interactions, and genetics,²⁵⁻²⁷ much fundamental information about methadone PK and PD remains missing. In addition, far more is known about the pharmacology of oral methadone used in high doses for the treatment of opioid addiction (80-160 mg daily) than about smaller intravenous doses used for acute pain (5-10 mg).

Based on known information, methadone, is clinically used as a racemic mixture, with R-methadone acting on the mu receptor, while both R- and S-methadone act to antagonize N-methyl-D-aspartate receptors.²⁸ The drug is lipophilic and has linear PK with a steady state volume of distribution ranging from 2-6 L/kg. Methadone is also 85-90% protein bound in plasma, primarily to alpha1-acid glycoprotein. Metabolism of methadone primarily occurs via CYP2B6 N-demethylation to inactive metabolites, primarily ethylidene-1,5-dimethyl-3,3-diphenylpyrrolidene (EDDP).²⁵ Methadone has a highly variable clearance, ranging from 3-10 L/h, and a terminal half-life of 8-59 hours. However, methadone persists in the liver and other tissues, with slow release sometimes resulting in prolonged duration of action.²⁹

Because of its potential prolonged duration of action, labeled dosing of intravenous (IV) methadone for use in opioid non-tolerant patients is 2.5-10 mg every 8-12 hours, slowly titrated to effect. Available data on methadone PK during treatment of acute pain are listed in **Table 2**.

Table 2. Methadone PK during treatment of acute pain

Study	Population (age)	Route	Dose	Substrate	Results

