6.7.4 PK Sampling Schedule

The total number of PK blood samples will be 18, 2 ml/sample, 36 ml (less than one-quarter cup). Blood will be centrifuged and plasma removed and stored at -70°C until shipment to a laboratory for analysis. The time of each sample collection should be recorded.

Table 4. Optimal PK sampling schedule relative to single dose of methadone

PK Time Point Sample Number	Elapsed Time After Dose (hh:mm)	
1	Baseline draw	
2	Start IV dose 0:00 + 0:01 ¹	methadone HCl 0.1 mg/kg bw IV push over 1 -2 minutes (including 3ml 0.9NS flush immediately following study medication administration)
3	0:05 ± 0:01	
4	0:10 ± 0:01	
5	0:15 ± 0:01	
6	0:30 ± 0:05	
7	1:00 ± 0:10	
8	1:30 ± 0:10	
9	2:00 ± 0:10	
10	4:00 ± 0:30 ²	
11	6:00 ± 0:30	
12	12:00 ± 0:30	
13	18:00 ± 0:30	
14	24:00 ± 0:30	

15	30:00 ± 1:00
16	48:00 ± 8:00
17	72:00 ± 8:00
18	96:00 ± 8:00

¹Immediately after starting IV dose

²Food can be served after the 4:00 sample collection.

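### Linear trapezoids after an IV push bias AUC upward on average, by about 0.2–4% depending on half-life; linear-up/log-down is a free, minor improvement

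*Combined protocol and SAP*

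**What the plan says.** Section 11.3.1 (Primary Analysis) plans a noncompartmental analysis in Phoenix WinNonlin in which "AUC will be calculated using the linear trapezoidal method". No other rule is given for falling concentrations. The same section estimates the elimination rate constant from the "slope of a log-linear least squares of at least 3 concentration–time points", so it treats the terminal phase as exponential when it estimates ke.

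Table 4 (section 6.7.4) gives the dose as "methadone HCl 0.1 mg/kg bw IV push over 1 -2 minutes" and states that "The total number of PK blood samples will be 18". The scheduled draws are at baseline, dose start, 5, 10, 15 and 30 minutes, then 1, 1.5, 2, 4, 6, 12, 18, 24, 30, 48, 72 and 96 h. The last three have windows of ±8 h.

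Two further rules in 11.3.1 bear on the point. On timing: "Nominal sampling time will be used in PK calculations, unless actual times are needed". On values below the limit after the peak: "half the quantification limit will be assigned for a single below-quantifiable-limit sample", or zero for consecutive ones.

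AUC and CL are both primary endpoints (section 11.1.1). Section 11.3.1 does not say how CL is derived, and the only AUC interval that it names is 0–24 h. It leaves further detail to a PK analysis plan that is not among the documents.

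**The concern.** After an IV push the concentration curve falls and is convex. A chord between two points on such a curve lies above it, so the linear rule adds area on every falling interval. The log rule is exact on a single-exponential segment.

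The added area depends on the gap between samples relative to the half-life. It is therefore largest in participants who eliminate the drug fastest, and it does not average out over about 20 participants. The background (section 2.1.1) expects "a terminal half-life of 8-59 hours", and it also says: "Methadone has a highly variable clearance, ranging from 3-10 L/h". At stake is a small, avoidable systematic error in a primary endpoint.

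**Working it through.** **1. The plan's own figure.** Section 11.6 says 15 participants give a 95% CI for CL within 60–140% of the geometric mean, at CVs of 23% and 38%. With a log-normal t interval, the limits are exp(±t × √ln(1+CV²)/√n), with t(0.975; 14) = 2.145.
- CV 23%: √ln(1.0529) = 0.227; 2.145 × 0.227/√15 = 0.126; CI 88–113%.
- CV 38%: √ln(1.1444) = 0.367; 2.145 × 0.367/√15 = 0.203; CI 82–123%.

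Both lie inside 60–140%, so 15 is adequate. The documents give no figure for AUC error.

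**2. One interval.** For C = exp(−bt) and a gap Δ, put x = bΔ. The ratio of linear to true area is (x/2)(1+e⁻ˣ)/(1−e⁻ˣ). For a half-life of 8 h, b = ln 2/8 = 0.0866.
- Δ = 24 h: x = 2.079, e⁻ˣ = 0.125; ratio 1.040 × 1.125/0.875 = 1.337.
- Δ = 18 h: x = 1.560, e⁻ˣ = 0.210; ratio 0.780 × 1.210/0.790 = 1.195.

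For Δ = 24 h the ratio falls to 1.037 at a half-life of 25 h and 1.007 at 59 h.

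**3. Whole profile, single exponential, half-life 8 h.** Excess area as a percentage of AUC0-inf (= 1/b = 11.54):

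| Interval (h) | Excess |
|---|---|
| 0–6 | 0.06% |
| 6–12 | 0.54% |
| 12–18 | 0.32% |
| 18–24 | 0.19% |
| 24–30 | 0.11% |
| 30–48 | 1.14% |
| 48–72 | 0.46% |
| 72–96 | 0.06% |
| Total | 2.9% |

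If the 48 h sample is missing, the linear area over 30–72 h is 42 × (0.07433 + 0.00195)/2 = 1.602, against a true 0.835. That excess is 0.767/11.54 = 6.6%, replacing 1.14 + 0.46 = 1.60%. The total becomes 2.9 − 1.6 + 6.6 = 7.9%.

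**4. With a distribution phase.** This uses C = A·exp(−at) + B·exp(−bt) at the nominal Table 4 times, tail C96/b, and true AUC0-inf = A/a + B/b. The distribution half-life (5–30 min) and A/B (1–9) are assumptions; the documents give neither.

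| Half-life | AUC0-inf, linear | AUC0-inf, linear-up/log-down | AUC0-inf, linear, 48 h missing | AUC0-24, linear |
|---|---|---|---|---|
| 8 h | +2.95 to +3.87% | +0.08 to +1.11% | +7.1 to +8.0% | +1.4 to +3.0% |
| 15 h | +2.15 to +2.92% | +0.04 to +0.77% | +6.6 to +7.0% | +0.5 to +2.0% |
| 25 h | +1.19 to +1.84% | +0.02 to +0.53% | +3.7 to +4.0% | +0.2 to +1.6% |
| 59 h | +0.23 to +0.60% | +0.01 to +0.25% | +0.6 to +1.0% | +0.1 to +1.4% |

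For AUC0-24, linear-up/log-down leaves at most +1.2% (half-life 8 h). Assumed three-exponential shapes give similar linear errors in AUC0-inf: +3.6 to +4.8% at 8 h and +0.5 to +0.6% at 59 h.

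**5. Clearance.** If CL = dose/AUC0-inf, the relative error is 1/(1+e) − 1. At 8 h that is 1/1.0295 − 1 = −2.9% to 1/1.0387 − 1 = −3.7%. In an illustrative population (three-exponential, median half-life 24 h, CV 38%), geometric mean CL is 1.7% low.

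**6. With realistic error.** Assumptions: distribution half-life 15 min, A/B = 3, 5% assay CV, sampling spread over the Table 4 windows, nominal times in the calculation.
- Half-life 8 h: mean AUC error +3.6% (linear) against +0.6% (log-down); root mean square error 4.2% against 2.3%. Linear AUC exceeds truth in about 95% of profiles.
- Half-life 59 h: linear AUC exceeds truth in about 53% of profiles. Root mean square error is about 9.3% with either rule.

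A harsher simulation used three-exponential curves, 5–10% assay CV and a first sample drawn before the full dose is in. The share above truth was 68–78% at 8 h, 65–69% at 24 h and about 50% at 59 h. In every simulated profile, linear AUC exceeded log-down AUC.

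**The case against.** The strongest reply is that the effect is slight, that other rules in the same section can matter more, and that the linear trapezoid is a recognised, prespecified method reported here only descriptively. Much of this stands.

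- **Every participant.** A reader might infer that each participant's AUC is too high and CL too low. That holds against the log-down AUC on falling intervals. It does not hold against true AUC, as step 6 shows.
- **Sample size.** A reader might infer that the sample size suffers because it is based on CL. A 1–2% shift in geometric mean CL is trivial against 60–140%, and section 11.6 rests on population PK techniques, which do not use trapezoids.
- **Spread of CL.** Because the bias depends on half-life, it narrows the spread of CL, but only by about half a percentage point: a true CV of 38% becomes about 37.5%, and 23% about 22.5% (assuming that CL varies through half-life).
- **Larger errors remain.** For a single exponential with half-life 25 h, drawing the 48 h sample 8 h early or late while using nominal time gives a total AUC error of +5.0% or −1.9%. Of this, +1.2% is the trapezoid rule, leaving +3.8% or −3.1% from timing. At 59 h about 30% of AUC is extrapolated. The change of rule cures neither.
- **Which AUC.** The 18–24 h gaps come after 30 h and do not touch AUC0-24, where the bias is smaller.
- **Unseen PK analysis plan.** It may specify another rule, but it would then contradict an explicit statement in the protocol, and the wording would still need correcting.

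These points limit the consequence. They do not remove the average upward bias, and they give no reason to prefer the linear rule.

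**Conclusion.** The point holds as a minor one. The prescribed rule overstates AUC on average. With the full schedule, the overstatement of AUC0-inf runs from about 3–4% at the shortest half-life the protocol cites to 0.2–0.6% at the longest. Linear-up/log-down removes most of it.

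The sizes rest on assumed distribution phases. The CL figures also rest on CL = dose/AUC0-inf, which the plan does not state. The bias is small beside the anticipated 23–38% CV, leaves the sample size intact, and does not fix the sign of any one participant's error.

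**What to change.** In section 11.3.1, replace the linear trapezoidal method with the linear-up/log-down trapezoidal method, and put the same rule in the PK analysis plan. Add that an interval ending in a value set to zero under the below-limit rule is integrated linearly, because the logarithm of zero is undefined.

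The cost is one software setting and a line or two of text. No sample, visit or participant is added.
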